11.2 Analysis of Adverse Events

11.2.1 Treatment-Emergent Adverse Events

Treatment-emergent adverse events (TEAEs) are defined as any event with an onset that is after the first dose of study drug and with an onset date within 105 days after the last dose of study drug in the analysis period, or prior to the first dose in the subsequent period for subjects who entered in to the subsequent period. Events where the onset date is the same as the study drug start date are assumed to be treatment-emergent, unless the adverse event start time is prior to the study drug start time with the following exception:

- If an AE onset date is the same as the first dose of Part B and the AE time is missing, the AE is considered TEAE for the Part A2.

If an incomplete onset date is collected for an adverse event, the event will be assumed to be treatment-emergent unless there is other evidence that confirms that the event is not treatment-emergent (e.g., the event end date is prior to the study drug start date).

Treatment-emergent adverse events (TEAE) for each safety population are defined as follows:

TEAEs of Safety_A1:

For subjects who do not enter Part A2, TEAEs are defined as any event with an onset after the first dose of study drug and no more than 105 days after the last dose of study drug.

For subjects who enter Part A2, TEAEs are defined as any event with an onset after the first dose of study drug and before the first dose of study drug in Part A2.

TEAEs of Safety_A2 for Subjects from ARM 1:

For subjects who do not enter Part B, TEAEs are defined as any event with an onset after the first dose of study drug in Part A2 and no more than 105 days after the last dose of study drug in Part A2.

For subjects who enter Part B, TEAEs are defined as any event with an onset after the first dose of study drug in Part A2 and prior to the first dose of study drug in Part B.

TEAE of Safety_ARM2:

TEAEs are defined as any event with an onset after the first dose of study drug in Part A2 or Part B and no more than 105 days after the last dose of study drug in the study.

TEAEs of Safety_B_NR:

TEAEs are defined as any event with an onset after the first dose of study drug in Part B and no more than 105 days after the last dose of study drug in the study.

TEAEs of Safety_B_R:

For subjects who do not receive retreatment with risankizumab, TEAEs are defined as any event with an onset after the first dose of study drug in Part B and no more than 105 days after the last dose of study drug in Part B.

For subjects who receive retreatment with risankizumab, TEAEs are defined as any event with an onset after the first dose of study drug in Part B and before the first dose of retreatment with risankizumab.

TEAEs of Safety_B_PBO_RT and Safety_B_RZB_RT:

TEAEs are defined as any event with an onset that is after the first dose of retreatment and no more than 105 days after the last dose of study drug.

TEAE of ALL_RZB:

TEAEs are defined as any event with an onset after the first dose of risankizumab through 105 days after the last dose of risankizumab, except for AEs with an onset during protocol-designed treatment gaps (i.e., placebo period) that was more than 105 days from the last dose of the previous risankizumab treatment and before the first dose of retreatment.

Summary tables will be presented as follows:

1. Adverse Event Overview

The number and percentage of subjects experiencing treatment-emergent adverse events will be summarized for the following adverse event categories:

- Any AE
- Any AE that was assessed as related to study drug by the investigator
- Any severe AE
- Any serious AE (SAE)
- Any serious AE that was assessed as related to study drug by the investigator
- Any AE leading to discontinuation of study drug
- Any AE leading to death
- Any deaths
- Areas of Safety Interest

2. Adverse Events by System Organ Class and Preferred Term

TEAEs will be summarized and presented using primary Medical Dictionary for Regulatory Activities (MedDRA) system organ classes (SOCs) and preferred terms (PTs). The SOCs will be presented in alphabetical order, and the PTs will be presented in alphabetical order within each SOC.

Subjects reporting more than one adverse event for a given MedDRA preferred term will be counted only once for that term (most severe incident for the severity tables and most related incident for the relationship tables). Subjects reporting

more than one type of adverse event within a SOC will be counted only once for that SOC. Subjects reporting more than one type of adverse event will be counted only once in the overall total.

In addition, the number and percentage of adverse events with causal relationship between the events and the study drug will be summarized using the same conventions described above.

3. Adverse Events by Maximum Severity

The severity grading of AEs follows Rheumatology Common Toxicity Criteria (RCTC).

- Grade 1 – mild
- Grade 2 – moderate
- Grade 3 – severe
- Grade 4 – life threatening

Adverse events will also be summarized by maximum severity. If a subject has an adverse event with unknown severity, then the subject will be counted in the severity category of "unknown," even if the subject has another occurrence of the same event with a severity present. The only exception is if the subject has another occurrence of the same adverse event with the most extreme severity (Life threatening). In this case, the subject will be counted under the "Life-threatening" category.

4. Adverse Events by Maximum Relationship

Adverse events will be summarized by maximum relationship to study drug, as assessed by the investigator. Relationship of an AE to study drug is assessed by the investigator and collected in the CRF as 'Yes' or 'No.' If a subject has an adverse event with unknown relationship, the subject will be counted in the relationship category of "unknown," even if the subject has another occurrence of the same event with a relationship of "No." If the subject has another occurrence

of the same adverse event with a relationship assessment of "Yes," the subject will be counted under the "yes" category.

A listing of all pretreatment (i.e., events start prior to the first study drug injection) serious adverse events will be provided.

The following tables are planned.

Treatment-emergent adverse events will be summarized as follows:

- Grouped by SOC and PT
- Grouped by SOC, PT and maximum relationship to study drug
- Grouped by SOC, PT and maximum severity

Treatment-emergent serious adverse events will be summarized as follows:

- Grouped by SOC and PT
- A by-subject listing will be provided

Pre-treatment serious adverse events will be summarized as follows:

- A by-subject listing will be provided

Treatment-emergent adverse events leading to death or premature discontinuation of study drug will be summarized as follows:

- Grouped by SOC and PT
- Separate listings by subject for deaths and premature terminations of study drug due to adverse events will be provided.

Treatment-emergent areas of safety interest will be summarized as follows:

- Grouped by SOC and PT
- A listing by subject will be provided.

Areas of Safety Interest:

Areas of Safety Interest groupings are listed in [Table 23](#). These events are of interest due to a higher rate in the moderate to severe psoriasis population, or of interest for all Ig products or products in general.

The final list will be based on the most updated final version of risankizumab Product Safety Statistical Analysis Plan, which is consistent to the most updated risankizumab Risk Management Plan.

Table 23. Areas of Safety Interest

ASI Grouping	Categories (ASI)	Search Criteria	Terms to Display	Include in AE Overview (Y/N)
Adjudicated CV Events	Major adverse cardiovascular events (MACE)	Adjudicated events	
Display underlined terms defined by the following adjudicated terms:
 
 • CV Death which includes CETERM values: Fatal CV, Fatal PE, Fatal Non-Cardiac/Non-Neuro Arterial Thrombosis/Thromboembolism, Undetermined Death, Not assessable death (cardiac/neuro/thrombotic), Fatal Stroke • Myocardial infarction • Stroke 	Y
	Extended MACE	Adjudicated events	
Display underlined terms from MACE and underlined terms below:
 
 • Hospitalization for Unstable Angina • Coronary Revascularization Procedures 	N

Table 23. Areas of Safety Interest (Continued)

ASI Grouping	Categories (ASI)	Search Criteria	Terms to Display	Include in AE Overview (Y/N)
Adjudicated CV Events (continued)	Other CV events	Adjudicated events	
Display underlined terms defined by the following adjudicated terms:
 
 • Thrombotic events which includes CETERM values: Deep Vein Thrombosis, TIA, Pulmonary Embolism, Non-fatal Non-Cardiac/Non-Neurological Arterial Thrombosis/ Thromboembolism, Other Venous Thrombosis, specified (non-fatal) • Cardiac arrhythmia which includes CETERM of: Clinically Significant Arrhythmia • Congestive heart failure which includes CETERM of Heart Failure • Hypertensive emergency 	N
Serious infections, TB, fungal and opportunistic infections (including herpes zoster)	Serious infections	Serious PTs of the CMQ (company MedDRA query) Infections (CMQ 80000018)	PTs	Y
	TB	Tuberculosis (including Investigations) CMQ (code 80000033)	PTs	Y
	Opportunistic infections	Opportunistic infections CMQ (code 80000073)	PTs	N

Table 23. Areas of Safety Interest (Continued)

ASI Grouping	Categories (ASI)	Search Criteria	Terms to Display	Include in AE Overview (Y/N)
Serious infections, TB, fungal and opportunistic infections (including herpes zoster) (continued)	Fungal infections	Fungal infections CMQ (code 80000063)	PTs	N
	Herpes Zoster	Herpes zoster CMQ (code 80000175)	PTs	N
Malignancies	All possible malignancies	Narrow – Malignancies (SMQ 20000090)	PTs	N
	Malignant Tumours	Narrow – Malignant tumours (SMQ 20000194)	PTs	Y
	Non-melanoma skin cancer (NMSC)	Broad – Skin malignant tumours (SMQ 20000204) excluding terms identified by the Melanoma CMQ (code 80000119)	PTs	N
	Malignant Tumours excluding NMSC	'Malignant Tumours excluding NMSC' is identified by the 'Malignant Tumours' search excluding terms identified by the 'Non-melanoma skin cancer (NMSC)' search.	PTs	Y

Table 23. Areas of Safety Interest (Continued)

ASI Grouping	Categories (ASI)	Search Criteria	Terms to Display	Include in AE Overview (Y/N)
Hypersensitivity Reaction	Hypersensitivity	Narrow – Hypersensitivity (SMQ 20000214)	PTs	Y – serious events only
	Anaphylactic Reaction	Narrow – Anaphylactic reaction (SMQ 20000021)	PTs	N
Hepatic Events	Hepatic Events	Broad – Hepatic failure, fibrosis and cirrhosis and other liver damage-related conditions (SMQ 20000013) Broad – Hepatitis, non-infectious (SMQ 20000010) Broad – Cholestasis and jaundice of hepatic origin (SMQ 20000009) Broad – Liver related investigations, signs and symptoms (SMQ 20000008) Narrow – Liver-related coagulation and bleeding disturbances (SMQ 20000015)	PTs	N

Adverse Event per 100 Patient-Years of Exposure

Adverse events occurring during the entire study will be presented by event rate per 100 patient-years. These will be presented for any TEAEs, serious adverse events, and Areas of Special Interest.

AEs per 100 patient-years of exposure is defined as the number of AEs divided by the total exposure in 100 patient-years. Note that one event per preferred term per day per subject will be counted in the calculation of the number of AEs (i.e., a preferred term will not be counted twice on the same day for the same subject). See the calculation method below.

$$100 \times \frac{\text{Number of TEAEs}}{\text{Total Patient Years}}$$

where total patient years is defined as the sum of the study drug exposure (defined as date of last dose – date of first dose + 105 days (5 half-lives)) of all subjects normalized by 365.25, and rounded to one decimal place.

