5.3.7 Adverse event collection and reporting

AE Collection

The following must be collected and documented in the eCRF by the Investigator:

- From signing the informed consent onwards through the Residual Effect Period until a patient's end of trial participation, all AEs (serious and non-serious), and AESIs must be collected.
- After the individual patient's completion of trial:
The investigator does not need to actively monitor the patient for AEs, but should only report relevant SAEs and relevant AESIs of which the investigator may become aware of.

The REP is defined as 15 weeks after the last trial medication administration. All AEs that occur during the treatment phase and throughout the REP will be considered as on treatment (see [Section 7.3.4](#)). Events that occur after the REP will be considered as post treatment events.

AE reporting to sponsor and timelines

The Investigator must report SAEs, AESIs, and non-serious AEs which are relevant for the reported SAE or AESI, on the BI SAE form via fax immediately (within 24 hours) to the Sponsor's unique entry point (country specific contact details will be provided in the ISF). The same timeline applies if follow-up information becomes available. In specific occasions the Investigator could inform the Sponsor upfront via telephone. This does not replace the requirement to complete and fax the BI SAE form.

In Japan, all SAEs and AESIs must be reported immediately to the head of the trial site. With receipt of any further information to these events, a follow-up SAE form has to be provided. For follow-up information the same rules and timeline apply as for initial information.

Information required

For each AE, the Investigator should provide the information requested on the appropriate eCRF pages and the BI SAE form, e.g. onset, end date, intensity, treatment required, outcome, seriousness, and action taken with the investigational drug(s). The Investigator should determine the causal relationship to the trial medication, and the trial procedures outlined under [Section 6.2](#).

The following should also be recorded as an (S)AE in the eCRF and SAE form (if applicable):

- Worsening of the underlying disease or of other pre-existing conditions
- Changes in vital signs, ECG, physical examination and laboratory test results, if they are judged clinically relevant by the Investigator.

If such abnormalities already pre-exist prior trial inclusion they will be considered as baseline conditions.

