7.3.4 Safety analyses

Adverse events will be coded using the Medical Dictionary for Drug Regulatory Activities (MedDRA) coding dictionary. Standard AbbVie summary tables and listings will be produced. All adverse events with an onset between start of treatment and end of the residual effect period (REP), a period of 15 weeks days after the last dose of trial medication, will be assigned to the treatment period for evaluation.

All treated patients will be included in the safety analysis. In general, safety analyses will be descriptive in nature and will be based on AbbVie standards. No hypothesis testing is planned.

Statistical analysis and reporting of adverse events will concentrate on treatment-emergent adverse events. To this end, all adverse events occurring between start of treatment and end of the residual effect period will be considered 'treatment-emergent'. Adverse events that start before first drug intake and deteriorate under treatment will also be considered as 'treatment-emergent'.

Frequency, severity, and causal relationship of adverse events will be tabulated by system organ class and preferred term after coding according to the current version of the Medical Dictionary for Drug Regulatory Activities (MedDRA).

Laboratory data will be analysed both quantitatively as well as qualitatively. The latter will be done via comparison of laboratory data to their reference ranges. Values outside the reference range as well as values defined as clinically relevant will be highlighted in the listings.

Treatment groups will be compared descriptively with regard to distribution parameters as well as with regard to frequency and percentage of patients with abnormal values or clinically relevant abnormal values.

Vital signs, physical examinations, or other safety-relevant data observed at screening, baseline, during the course of the trial and at the end-of-trial evaluation will be assessed with regard to possible changes compared to findings before start of treatment.

More information on the analysis of safety will be given in the TSAP.

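### SAP 11.2.1 defines treatment-emergent adverse events by onset alone and, without saying so, drops the protocol's rule for pre-dose events that worsen on treatment

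*SAP*

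**What the plan says.** **Protocol 7.3.4** has two components. The onset component says that "all adverse events occurring between start of treatment and end of the residual effect period will be considered" treatment-emergent. The worsening component follows: "Adverse events that start before first drug intake and deteriorate under treatment will also be considered as" treatment-emergent. Protocol 5.3.7 sets the length of the residual effect period: "The REP is defined as 15 weeks after the last trial medication administration".

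**SAP 11.2.1** opens with a general definition: "Treatment-emergent adverse events (TEAEs) are defined as any event with an onset that is after the first dose of study drug", with onset no later than 105 days after the last dose in the analysis period, or before the first dose of the next period. Separate definitions follow for Safety_A1, Safety_A2, Safety_ARM2, Safety_B_NR, Safety_B_R, the two retreatment populations and ALL_RZB. Each turns on onset; for ALL_RZB, for example, "TEAEs are defined as any event with an onset after the first dose of risankizumab through 105 days after the last dose of risankizumab". None mentions worsening.

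The same section handles serious events with an earlier start separately: "A listing of all pretreatment (i.e., events start prior to the first study drug injection) serious adverse events will be provided".

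**SAP 14.1** lists four changes from the protocol. The treatment-emergent definition is not among them.

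**The concern.** The two documents classify the same event differently, and nothing tells the reader which definition governs. Adverse events are collected from informed consent (Protocol 5.3.7). Screening lasts 7 to 42 days and is used partly to taper disallowed medication (Protocol 6.2.1), so events with a pre-dose onset are foreseeable.

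If such an event is kept as one record and worsens after dosing, the SAP rule removes it from every table built on TEAEs. A serious one is then described by when it began and not by when it deteriorated. The report's TEAE counts would not match the definition in the protocol it cites.

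**Working it through.** No sample size, power or alpha figure is involved. The check is a comparison of the two texts.

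**1. The post-dose window.** Protocol: 15 weeks × 7 = 105 days. SAP: 105 days. The window carries over unchanged, so the missing worsening rule is a separate difference.

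**2. The definitions side by side.**

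| Event | Protocol 7.3.4 | SAP 11.2.1 |
|---|---|---|
| Starts after first dose, within the window | Treatment-emergent | Treatment-emergent |
| Starts before first dose, does not worsen | Not treatment-emergent | Not treatment-emergent |
| Starts before first dose (complete date), worsens on treatment, one record | Treatment-emergent | Not treatment-emergent |

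Only the third row differs.

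**3. Whether another SAP rule restores the third row.**
- The same-day rule counts an event starting on the first dosing date "unless the adverse event start time is prior to the study drug start time". That is still a test of onset.
- The partial-date rule is generous: "If an incomplete onset date is collected for an adverse event, the event will be assumed to be treatment-emergent", absent contrary evidence. It does not help when the pre-dose date is complete.
- No other SAP section makes worsening of a pre-dose event a criterion.

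**4. Whether the departure is declared or explained by version.** SAP 3.0 cites the protocol of 28 July 2016. The log for the 11 October 2016 amendment describes the change to 7.3.4 only as a move to AbbVie tables and standards, and the current 7.3.4 keeps the worsening sentence. A version difference therefore does not appear to explain the omission. In SAP 11.3.2, where laboratory grading departs from the protocol, the SAP says so and gives a reason. Here it does not.

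**5. Which outputs are affected.** Under SAP 11.2.1 these are the TEAE overview, the organ-class and preferred-term tables, the maximum-severity and maximum-relationship tables, and the TEAE rate per 100 patient-years. The pretreatment SAE listing would include a serious third-row event on its start date alone.

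**6. Size.** The documents give no rate of screening-period events or of their worsening, so the count cannot be derived. As illustration only, assume 10% of 500 patients have a pre-dose event and 5–10% of those worsen:
- 500 × 0.10 × 0.05 = 2.5 patients; 500 × 0.10 × 0.10 = 5 patients, which is 0.5–1% of 500.
- Split 4:1, that is 2–4 on risankizumab and 0.5–1 on placebo.

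Both inputs are assumptions, and the result scales in proportion to each.

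**The case against.** The strongest reply is that data collection already closes most of the gap. Protocol 6.2.1 puts chronic diseases, current conditions and screening findings on the Baseline Condition page, and Protocol 5.3.7 requires worsening of the underlying disease or a pre-existing condition to be recorded as an (S)AE. If that record is dated at the worsening, the SAP's onset rule captures it. This stands as a limit on size. It does not remove the point: the documents do not say which onset date applies, or that a worsening event already on the AE page must be split into a new record. Capture then depends on site practice.

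A reader might also infer that serious worsening disappears from the report or is only listed as pretreatment. The documents do not support that. SAP 11.2.2 lists deaths and all SAEs, and summarises SAEs and events leading to discontinuation by organ class and preferred term, with no stated treatment-emergent restriction. How this fits with the treatment-emergent SAE and discontinuation tables in 11.2.1 is unclear. Laboratory and vital-sign worsening is also assessed against baseline regardless of TEAE status (SAP 11.3 and 11.4).

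A reader might further infer that an event starting in Part A and worsening in Part B is wrongly left out of Safety_B_R. The protocol sentence covers only events that begin before first drug intake. An event that begins after dosing in Part A is already treatment-emergent in the period where it started, and counting it again in Part B is not something the protocol asks for.

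Finally, in Part A1 the same rule applies to both randomised, blinded arms, and Protocol 7.3.4 plans no hypothesis tests on safety. Nothing in the documents shows a distortion between arms.

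**Conclusion.** The point holds as an undeclared contradiction between Protocol 7.3.4 and SAP 11.2.1. It concerns counts and labels for a narrow class: events that start before first drug intake, are kept as one record with a complete original onset date, and deteriorate after dosing.

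The number is probably small; the illustrative 2.5–5 patients is not evidence of size. It is tempting to suppose that the lost events fall mainly in the severe and serious rows, but a change from grade 1 to grade 2 is also deterioration and enters neither.

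One reading remains open. If first drug intake means first risankizumab, the omission also affects ALL_RZB and Safety_ARM2 for an event that starts on placebo in Part A1 and worsens after the Week 16 switch. If it means first study drug of either kind, it does not.

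**What to change.** - In SAP 11.2.1, restore the protocol rule: an event starting before first study drug intake that deteriorates under treatment, within the 105-day window, is treatment-emergent. State whether first drug intake means first risankizumab for ALL_RZB and Safety_ARM2, and apply the rule there if so.
- State how worsening is identified from the data actually collected, for example by a new AE record dated at the worsening. The documents do not show that dates of grade change or of becoming serious are collected, so the rule should not depend on them unless the eCRF is confirmed to hold them.
- In the pretreatment SAE listing, flag any event that deteriorated after the first dose.
- If the onset-only definition is intended, declare and justify it in SAP 14.1.

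The cost is SAP wording and minor programming. TEAE rates may rise slightly.

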10.1.3 Analyses of Time-to-Event Variables

Time to first achievement of endpoints will only be performed in ITT_A1 up to Week 16. The time to event will be calculated as:

- Time to first achievement (with observed event) = [date of first achievement] – [date of first dose] + 1
- If a subject never attains Endpoint at the end of evaluation period, that subject's time to first achievement will be censored at the last visit where the variable was measured

Time to loss-of-response (and time to relapse) endpoints will only be performed in ITT_B_R Population among those who achieved response at Re-Randomization. The time to failure events will be calculated as:

- Subjects will be considered as failures if they subsequently lost the response, or discontinue from the study due to AE of "Worsening of disease under study," or receive retreatment with risankizumab.
- Time to failure events = [date of failure] – [date of first dose in Part B] + 1
- Subjects who maintain Endpoint throughout the study, or discontinued from the study due to reasons other than above, will be censored at their last measurement.

Both time to first achieving endpoints and time to loss-of-response endpoints will be analyzed using Kaplan-Meier estimates for each treatment group. In the ITT_A1 and ITT_B_R populations, treatments will be compared using stratified Log-rank test.

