- Imputation of missing data. The imputation will be generated for each efficacy endpoint measurement. The variables to be included in the imputation model are: Baseline disease severity (PASI and sPGA), Baseline weight (continuous variable), treatment group, actual prior TNF antagonist exposure, and measurements at each visit from randomization (or re-randomization) up to the end of the analysis period. For each endpoint, 20 'complete' datasets will be generated using SAS PROC MI. The imputed post-baseline measurements

will be rounded to the same precision as the observed data before the determination of responder status (e.g., PASI 90).

- Analysis of imputed data sets. A CMH test, stratified by stratification factors, will be used to analyze categorical endpoints in each imputed dataset.
- Synthesis of imputation and analysis results. SAS PROC MIANALYZE will be used to generate the final inferences of the risk difference between treatment groups.

Of note, subjects who discontinued due to AE of "Worsening of disease under study," or received retreatment with risankizumab for relapse during Part B, will be counted as non-responders in all visits thereafter in the NRI and MI analyses, and will have their last observation prior to discontinuation or retreatment with risankizumab carried forward in the LOCF analyses.

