11.0 Safety Analysis

11.1 General Considerations

Safety analyses will include adverse events, laboratory, local tolerability, ECG, and vital sign measurements. Safety summaries will be provided using the safety population in each period as defined in Section 5.1. Comparison between risankizumab group and placebo group will be performed in the Safety Population in Safety_A1 and Safety_B_R populations. Continuous variables will be analyzed using one-way ANOVA and

categorical variables will be analyzed using Fisher's exact test. For analyses of AEs, only P values ≤ 0.100 when rounded to three digits will be presented.

Missing safety data will not be imputed.

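### The Part B adverse-event contrast mixes psoriasis worsening with harm and stops counting at retreatment, so its pooled rows cannot be read as a safety comparison and the net direction of bias is unknown.

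*SAP*

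**What the plan says.** Protocol 5.3.7 lists, among the items to be recorded as an (S)AE, "Worsening of the underlying disease or of other pre-existing conditions". It makes no exception for protocol-defined relapse (sPGA of 3 or more).

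SAP 11.2.1 sets the Safety_B_R window in two ways. For patients who are retreated it is "any event with an onset after the first dose of study drug in Part B and before the first dose of retreatment with risankizumab". For those who are not, it runs from the first Part B dose to "no more than 105 days after the last dose of study drug in Part B". Neither definition excludes or separates any term.

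SAP 11.1 states: "Comparison between risankizumab group and placebo group will be performed in the Safety Population in Safety_A1 and Safety_B_R populations". It adds that "categorical variables will be analyzed using Fisher's exact test" and that AE p-values of 0.100 or less are printed. Protocol 7.3.4, by contrast, describes the safety analysis as descriptive with no hypothesis tests.

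The SAP expects psoriasis to be reported as an AE. Section 10.1.3 counts discontinuation for an AE of "Worsening of disease under study" as an efficacy failure, and section 10.1.4 uses the same term.

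**The concern.** In Part B, worsening after withdrawal is the efficacy outcome under study. Protocol 7.7 assumes that at most 10% of patients kept on risankizumab and about 25% of those switched to placebo lose response by Week 52. If worsening is also entered as an AE, one event counts as loss of efficacy in SAP section 10 and as harm in section 11.

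The rows at risk are those that pool terms: any AE, severe AE, serious AE and the organ-class totals. Safety_B_R is one of only two populations in which the arms are compared for safety, and one of three that receive complete safety tables (SAP 5.1). A difference there would be read as a safety finding.

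A second feature of the same definition works in the opposite direction. A patient who relapses leaves the window at first retreatment, and more of these patients are on placebo. The AE overview reports percentages of subjects, so the arm with shorter follow-up has less chance to show an unrelated event.

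**Working it through.** **Plan's own figure.** The documents give no AE rate. The only figure for the Part B groups is the sample size in Protocol 7.7: 90% v 75% response, ratio 1:2, 90% power, two-sided 0.05. With pooled variance and a mean response of (0.90 + 2 × 0.75)/3 = 0.80:

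n = [1.960 × √(0.80 × 0.20 × 1.5) + 1.2816 × √(0.09 + 0.1875/2)]² / 0.15² = (0.960 + 0.549)² / 0.0225 ≈ 101.3, so 102.

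That gives 102:204, and 306/0.8 = 382.5, so 383. Both match the plan.

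**Inputs for the AE illustration**

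- Relapse by Week 52 (24 weeks of Part B): 10% risankizumab, 25% placebo. These are the Protocol 7.7 loss-of-response rates. Loss of sPGA 0 or 1 includes patients at sPGA 2, so they overstate relapse.
- Assumed: the risk u of a non-psoriasis AE over 24 weeks is the same in both arms (50%, varied from 20% to 60%); hazards are constant; there is no other dropout.
- Unknown: f, the share of relapses entered as a Safety_B_R event. Neither document gives it.

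**Formula.** Let B = -ln(1-u), R = -ln(1-r) and S = B + R, where r is the relapse risk. With follow-up ending at relapse:

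- P(other AE seen) = (B/S)(1 - e^-S)
- P(relapse with no earlier AE) = (R/S)(1 - e^-S)
- P(any AE) = first + f × second

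**At u = 50% (B = 0.6931)**

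- Risankizumab: R = 0.1054, S = 0.7985, 1 - e^-S = 0.550. Other AE 0.4774; relapse first 0.0726.
- Placebo: R = 0.2877, S = 0.9808, 1 - e^-S = 0.625. Other AE 0.4417; relapse first 0.1833.

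Placebo minus risankizumab = -0.0357 + 0.1107 f:

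- f = 0: -3.6 points
- f = 0.5: +2.0 points
- f = 1: 62.5% - 55.0% = +7.5 points
- sign change at f = 0.0357/0.1107, about 0.32

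**Other background risks, same 24 weeks**

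| u | gap at f = 0 | gap at f = 1 | sign changes at f |
|---|---|---|---|
| 20% | -1.5 | +12.0 | 0.11 |
| 40% | -2.9 | +9.0 | 0.25 |
| 50% | -3.6 | +7.5 | 0.32 |
| 60% | -4.1 | +6.0 | 0.41 |

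**Full Part B.** Carry the same relapse hazards over 60 weeks plus a 15-week tail, with u now the risk over 60 weeks. Mean follow-up is 64 weeks on risankizumab and 50 on placebo. The gap at f = 0 is -4.4, -8.2 and -11.0 points for u = 20%, 40% and 60%. At f = 1 it is +21.3, +14.9 and +8.9. This extrapolates a Week 52 assumption.

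**Effect on the test.** The planned 400 patients give 400 × 0.8 = 320 re-randomised, or 213 placebo and 107 risankizumab. At u = 50% and f = 1 (62.5% v 55.0%), Fisher's test gives p of 0.05 or less in about 24% of trials with no true difference in non-psoriasis risk. A psoriasis row at 25% v 10% would do so in about 91%, and that result would be the efficacy finding.

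**The case against.** A reader might infer that the plan makes risankizumab look safer than it is. The case against that reading is strong, and most of it stands.

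- **Direction.** Closing the window at retreatment favours placebo. Below f of about one third (at u = 50%), the net bias runs against risankizumab.
- **Risankizumab's own percentages are not lowered.** Its relapses count too; only the contrast with placebo is distorted.
- **Relapse may fall outside Safety_B_R.** Open-label drug is dispensed as soon as relapse is entered (Protocol 6.2.2). Under SAP 11.2.1, an event dated on a drug start date belongs to the period that starts that day unless its start time is earlier. The only exception concerns the first Part B dose. A relapse dated on the first retreatment day with no time can therefore move to the retreatment period. Earlier onsets, and worsening to sPGA 2 (which triggers no retreatment), stay in.
- **Relapse is not equated with the AE.** SAP 10.1.3 and 10.1.4 name retreatment separately from discontinuation for a disease-worsening AE. This weakens the assumption that every relapse is reported as an AE, but does not cancel Protocol 5.3.7.
- **Psoriasis terms are visible.** Preferred-term tables show them on their own lines, also by severity and for serious events. The pooled rows still cannot be rebuilt from those lines, because a subject with several events is counted once in a total.
- **Discontinuation row.** Relapse leads to retreatment rather than withdrawal, so mixing there is likely to be small.

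Larger gaps could be produced by supposing, say, 50% v 10% worsening by Week 88, but neither document supports such rates.

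**Conclusion.** The concern holds in a limited form. As written, the pooled rows of the randomised Part B AE contrast combine loss of efficacy with harm and are also affected by unequal follow-up. These are opposing artefacts of unknown size, so a difference in either direction, or no difference, cannot be interpreted from those rows alone.

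By Week 52, on a 50% background risk and the plan's 25% v 10% as an upper proxy for relapse, the artefact lies between -3.6 and +7.5 points. Those limits rest on equal true non-psoriasis risk, constant hazards and no other dropout. The documents do not settle where in the range the trial would fall, and they do not support a claim that risankizumab is systematically flattered. The efficacy analyses are not affected. This is a worthwhile, low-cost improvement held with moderate confidence.

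**What to change.** Before database lock, add to SAP 11.2.1:

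1. A fixed list of preferred terms that count as worsening of the disease under study.
2. For Safety_B_R, keep the planned AE overview and the organ-class and preferred-term tables. Add a supplementary set without the listed terms, and show disease-worsening AEs separately by arm. The supplementary set should not replace the planned tables: that would hide real flares after withdrawal and leave the follow-up imbalance in place.
3. AE rates per 100 patient-years by arm for Safety_B_R, with time at risk ending at first retreatment. The SAP specifies such rates only for the study as a whole.
4. An explicit period assignment for AEs dated on the first retreatment day with no start time, parallel to the existing exception for the first Part B dose.

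The cost is SAP wording, a short term list and a few more tables. No new data are needed.
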